5 POTENTIAL RISKS AND BENEFITS TO HUMAN SUBJECTS

Participants may or may not derive a direct benefit of the study. Participants will benefit from having had the opportunity to try scleral lenses (non-coated and Hydra-PEG coated), which is one of the newest lenses designs in the market for vision correction. If there is a benefit that the participants report, then they will be permitted to keep a pair of scleral lenses, so far as they continue to seek care from UW-CLC or their own contact lens specialist.

This study gives insight to eye care providers on whether non-surface coated, or surface coated scleral contact lens have the capacity to improve the ocular physiology, reduce dryness, and improve the quality of life in patients with dry eyes. This study may benefit optometric practitioners and clinical scientists on a potential new option to reconsider non-pharmacological agents such as contact lenses as one of the possible options for treating/managing dry eye conditions. This knowledge will help practitioners make informed decision for their dry eye patients based on clinical ocular surface characteristics/findings of their patients vis-à-vis lens design, material, surface treatment/modification, wearing schedule and the technology involved in producing these lenses. This is so because different lenses have different interactions with the front surface of the eye and with the improved designs and chemistry, contact lenses may lead to a new path in the management for dry eyes. Participation in this study may also contribute to scientific research information that may be used in the development of new contact lenses based on the chemistry of the material, surface treatment options and interaction with pre-corneal tear film. This may help provide improved comfort and reduce contact lens wear dropouts. The optometric community will benefit as they will have a better understanding of how selection of either non-coated or coated scleral contact lenses could make a significant impact in regaining and maintaining the integrity of the ocular physiology, thereby improving comfort for dry eye patients.

This study is considered a non-significant risk study based on United States Food and Drug administration (FDA) and International Standards Organization (ISO) guidelines due to the daily wear of the lenses in the study.

The scleral lenses to be used in this study are approved by Health Canada and are commercially available. The lenses are intended for daily wear (NOT extended wear). Because this study is a dispensing study, participants' lens wear will be monitored closely by the investigators. Participants can contact the investigator by phone and email at any time throughout the study.

Complications that may occur during the wearing of contact lenses include discomfort, dryness, aching or itching eyes, excessive tearing, discharge, hyperemia (redness) and variable or blurred vision. More serious risks may include photophobia, iritis, corneal edema or eye infection. Although contact lens-related infections are very infrequent with GP contact lenses, the possibility does exist. The occurrence rate of incurring a bacterial infection for patients that wear GP contact lenses is approximately 2/10,000 per year. (5)

If the participant should experience any pain or discomfort during lens wear, any of the symptoms described above, or there is any health concern or a case of emergency, they are instructed to contact CORE at [contact] or [REDACTED] ([contact] [name], using the information on the wallet card. (Appendix 18)

Although participants with any known allergies or sensitivity to the diagnostic pharmaceuticals products or drops such as fluorescein, used in this study would have been excluded, if any irritation occurs, the participant will be instructed to contact the investigators.

Instruments to be used in this study are ophthalmic instruments used frequently in a clinical environment and thus pose no risks to the participant. The Spectralis OCT has been classified as a NSR (non-significant risk) device based on United States Food and Drug Administration (FDA) guidelines. In OCT imaging, all exposures to light from the semiconductor optical amplifier (SOA) source are kept within documented safe limits. The light from the SOA source that will be used for optical ranging will be at the infrared. The limits for safe ocular exposure to laser light have been well established and are documented by the American National Standards Institute, ANSI Z136.1-1993. The ANSI standard for maximum permissible exposure (MPE) for 1300 nm light is 4.9 mW assuming full pupil intrabeam viewing (7 mm pupil aperture) for long exposure times (up to 103 seconds) with the light being focused on the retina. The real time OCT system will comply with this standard, which is especially conservative in our case, since in anterior segment OCT, light is focused on the cornea, so that the light reaching the retina is out of focus. The output light can be set up to 1.4 mW and the actual measured output is 1.14 mW, which is well below ANSI Z136.1-2000 standards for safety. Therefore, the measurement is non-invasive and safe.

Parts or all of this study will be conducted during the COVID-19 pandemic. Therefore, risks of infection with COVID-19 exist through participation. These risks arise due to possible exposure during commute to and from the study visit as well as during the study visit, particularly due to the closeness of the investigator and participant (within 2m for some assessments). The potential effects of COVID-19 are not yet fully known and may include long-term health consequences. In a small percentage, infection with COVID-19 can lead to serious illness, hospitalization, and in rare cases to complications leading to death. Individuals aged 60 and above and those with underlying medical conditions are considered at a greater risk for severe illness from the COVID-19 virus.

In consideration of risks associated with COVID-19, CORE has implemented a series of on-site safety procedures which have been reviewed and approved by the University of Waterloo. These include, but are not limited to, self-screening of investigators and participants prior to entering the building, maintaining physical distancing as much as possible, frequent handwashing, wearing of face masks by the investigator and participant, and frequent room and equipment hygiene and decontamination.

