3 OBJECTIVES

The specific objectives are:

1. To evaluate the impact of coated and non-coated scleral contact lenses on DE symptoms.
2. To assess the impact of the lenses on ocular surface health.
3. To measure the comfort and quality of life ratings of each lens type.
4. To determine the subjective ratings of each pair of lenses.

The primary outcome variables are:

1. Epithelial and corneal thickness
2. Quality of the tear film (osmolarity)
3. Levels of protease (inflammatory markers)
4. Contact Lens Impact on Quality of Life (CLIQ) questionnaire score
5. Contact Lens Questionnaire-8 (CLDEQ-8) questionnaire score

Other variables of interest:

- Hours of wear
- Subjective ratings of comfort, dryness, vision and burning.

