4 MATERIALS AND METHODS

4.1 STUDY DESIGN

4.1.1 OVERALL DESIGN

This will be a prospective, dispensing cross over study design involving five visits.

The first visit will involve screening, baseline measurements and trial fitting of scleral lenses. At this visit, participants may be wearing their habitual contact lenses (if any) as prescribed by their Optometrist/Ophthalmologist.

The second visit will be a dispensing visit of one of the pairs of the scleral contact lens designs (with or without Hydra-PEG, randomly assigned) and a single follow up visit after 8-10 hours of lens wear in a day, four weeks later (third visit). A washout period of a minimum of 48 hours will be applied between lens types. The fourth and fifth visits will be for the other scleral contact lens visits (delivery and after 4 weeks).

Scleral contact lenses to be worn in this study will be made of Boston XO material (with and without Hydra PEG) approved by Health Canada for commercial purposes. The scleral contact lenses will have a diameter of 14.8-15.4mm. The manufacturer's recommended guidelines will be used to select and fit these lenses, with an expected corneal clearance between 250 μ m to 350 μ m. As to which of the two scleral contact lenses are being assessed, both the investigator and the participant will be masked as the Optometric assistant will provide the lenses in an unlabelled case.

Masking the investigator will prevent bias when measuring the primary outcome variables and analyzing the data.

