4.3.11 STUDY QUESTIONNAIRES-ANALOG RATING SCALES

The following questionnaires will be used in the study.

As part of the recruitment and the baseline measurements (screening visit), Ocular Surface Disease Index (OSDI) and Standardized Patient Evaluation of Eye Dryness (SPEED) questionnaires will be used to determine the severity and frequency of the DE condition. It will also be used to determine eligibility of the participants (Appendix 4 and 5). Contact Lens Dry Eye Questionnaire 8 (CLDEQ-8) will be used to assess ocular symptoms with the scleral contact lenses at the end of each study visit. (Appendix 8) Contact Lens Impact on Quality of Life (CLIQ) will be used to assess the impact of contact lenses on their daily lives during the wearing schedule. The Contact Lens Dry Eye Questionnaire 8 (CLDEQ-8), Contact Lens Impact on Quality of Life (CLIQ) (Appendix 9) and wearing habit/experience log along with the subjective grading scales (Appendix 10) will be given to the participants to fill out for each week wearing the scleral lenses. The questionnaires will be returned to the investigator during the follow up visits. The standard method of recording the CLIQ questionnaire will be used in the study.

Comfort, vision, dryness, burning and overall preference rating scales (0-100) will be used to assess the subjective responses for each of the contact lenses. These subjective ratings will be done on a weekly basis (at home) and at the end of each study visit.

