8 STUDY COMPLETION AND REMUNERATION

Once their involvement in the study is complete, participants will be informed about receiving feedback following study completion in the Letter of Appreciation (Appendix 11).

Participant remuneration will be \$180 for completing the study and is typically paid at the end of the study (Appendix 12). This remuneration can be in a form of cheque or Amazon gift card and participants will be asked to choose one of the two options. One pair of the study lenses may be kept by participants at the end of the study as long as they continue care with UW-CLC or their own contact lens specialist.

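### Section 5 ties keeping a pair of study lenses to a reported benefit and section 8 does not; if participants are told the section 5 version, self-reports may be biased towards benefit

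*Combined protocol and SAP*

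**What the plan says.** Two sections state when a participant may keep study lenses. Section 5 (potential risks and benefits) says "If there is a benefit that the participants report, then they will be permitted to keep a pair of scleral lenses", and adds that care must continue at the university clinic or with the participant's own specialist. Section 8 (study completion and remuneration) says "One pair of the study lenses may be kept by participants at the end of the study as long as they continue care", with the same choice of care provider and no mention of benefit.

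Section 3 lists five primary outcome variables. Two are questionnaire scores: "Contact Lens Impact on Quality of Life (CLIQ) questionnaire score" and "Contact Lens Questionnaire-8 (CLDEQ-8) questionnaire score". The first objective is "To evaluate the impact of coated and non-coated scleral contact lenses on DE symptoms". Section 4.3.11 adds 0-100 self-ratings of comfort, vision, dryness, burning and overall preference. On the home questionnaires it says "The questionnaires will be returned to the investigator during the follow up visits".

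On design, section 4.1.1 says "This will be a prospective, dispensing cross over study design involving five visits". On masking, it says "both the investigator and the participant will be masked as the Optometric assistant will provide the lenses in an unlabelled case".

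No section says how, when or to whom a benefit is to be reported, or whether the questionnaires count as such a report.

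**The concern.** Followed as written, section 5 attaches something of value to a favourable self-report, in a trial that relies heavily on self-report. A participant who knows the condition and wants the lenses has a reason to answer more favourably than they otherwise would.

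The exposure is greatest for statements about scleral wear as such. Section 1 says a study is needed of how effective scleral wear is in typical dry eye patients. Section 2 plans assessment before and after wear. Section 5 expects insight into whether either lens can reduce dryness and improve quality of life. Every participant wears scleral lenses in both periods, so the design contains no group in which a response shift could be seen and subtracted.

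**Working it through.** The plan gives no figure to reproduce on this point. The check sets the passages side by side, traces how the condition could reach the data, and works out which comparisons it would affect.

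**1. The two conditions**

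| | Section 5 | Section 8 |
|---|---|---|
| Reported benefit | Stated as a condition | Not mentioned |
| Continued care | Required | Required |
| What is kept | A pair, coating not specified | One pair, coating not specified |

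The rows differ only on reported benefit. A participant who reports none but continues care qualifies under section 8 and, on the natural reading, not under section 5.

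**2. Which outcomes are exposed**

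Two of the five primary outcomes (CLIQ, CLDEQ-8) and all the 0-100 ratings are self-reported. Thickness, osmolarity and protease are instrument or assay readings and are not directly exposed.

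**3. How the condition could reach the answers**

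Three links are needed.

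- The participant knows the condition. This cannot be checked, because the consent letter (Appendix 2) is not in the text available for review.
- The participant believes that study answers count as a report of benefit. No section says so, but the inference is reasonable. The questionnaires, log and ratings are the scheduled means of describing experience. They are handed to the investigator, and in Table 2 their review is the last row before study exit. Section 7 also lets symptoms shown on the questionnaires inform discontinuation.
- The participant wants the lenses. This is unknown.

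**4. Effect on each comparison**

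Let the reported score equal the true score plus a shift *b*, with *b*C under the coated lens and *b*U under the uncoated lens.

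- Absolute level under a lens: reported mean = true mean + *b*. The whole shift remains, and without an unlensed arm it cannot be separated from true benefit.
- Lens difference: reported difference = true difference + (*b*C − *b*U). If the shifts are equal, the second term is zero.

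**5. How far the cancellation holds (assumed inputs, for illustration only)**

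*Equal shift on a bounded scale.* Assume 0-100 ratings with means 75 and 82, SD 15 and within-person correlation 0.5. Before truncation the SD of the difference is 15 × √(2 × (1 − 0.5)) = 15, so the standardized difference is 7/15 = 0.47. With scores cut off at 0 and 100 (200,000 simulated pairs):

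| Equal upward shift | Mean difference | Standardized difference |
|---|---|---|
| 0 | 6.50 | 0.46 |
| 10 | 5.39 | 0.43 |
| 20 | 3.75 | 0.37 |

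The ceiling costs some sensitivity but creates no false difference.

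*Unequal shift.* Take a paired t-test with n = 20 (the planned completers), two-sided 0.05 (sidedness assumed) and no true difference. Let δ = (*b*C − *b*U) / SD of the paired difference. The rejection rate follows from the noncentral t with 19 degrees of freedom and noncentrality δ√20:

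| δ | δ√20 | Rejection rate |
|---|---|---|
| 0.1 | 0.45 | 7% |
| 0.2 | 0.89 | 14% |
| 0.3 | 1.34 | 25% |

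False positives rise only if the shift differs by lens. That would need masking to fail, or the incentive to act differently by period in a way that does not balance across sequences. Nothing in the documents indicates either.

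**The case against.** The strongest reply is that this is loose wording in a risk-benefit narrative. Section 8, which deals with completion and remuneration, carries no such condition. Section 5 says if, not only if, and section 8 is permissive, so the two are inconsistent without flatly contradicting each other. That stands as to wording. Still, a condition that excluded nobody would have no purpose, so the restrictive reading is the natural one.

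The incentive may also be weak. The $180 payment matches $20 per hour for the 9 visit hours in Table 1 and does not depend on benefit. A participant who gains nothing has little use for lenses fitted to their own eyes. This is fair, and it is one reason why no size can be given.

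A reader might infer that the plan rewards good CLIQ or CLDEQ-8 scores. The documents do not support that, since no text connects the reported benefit to those instruments. A reader might also infer that poor ratings of the worse lens are discouraged. That does not follow either: the reward is a pair, so someone who rates one lens badly and reports benefit from the other still qualifies. Nor does section 5 assert that the lenses relieve dryness or improve quality of life. It asks whether they can, and says participants may not benefit directly.

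Finally, Table 2 lists OSDI and SPEED, but not CLIQ or CLDEQ-8, at Visit 0-0. The two exposed primary outcomes therefore have no baseline listed there for a before-after estimate. This limits the formal analyses affected. It does not protect descriptive statements about how participants fared in scleral lenses.

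**Conclusion.** The inconsistency between sections 5 and 8 is certain from the text. The bias is conditional: it requires that participants are told the section 5 version and take their study answers to count as a report of benefit. If so, absolute conclusions about symptoms or quality of life under scleral wear may be too favourable, and no analysis in section 9.1 could detect or correct this.

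The documents do not support reading this as a bias towards the coated lens. The incentive attaches to either lens, both are worn under masking, and an equal shift cancels in the paired difference apart from a modest ceiling effect under the assumed inputs. The size of any shift cannot be derived from the documents, and a figure in scale points would be a guess. The point is worth acting on because the incentive is avoidable and cheap to remove before data are collected.

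**What to change.** Reconcile sections 5 and 8 and the consent letter so that eligibility to keep a pair does not depend on anything the participant reports in the study. One way is to remove the reported-benefit condition from section 5, leaving the continued-care condition that both sections share. State in the consent letter that questionnaire and rating answers have no bearing on keeping lenses.

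The amendment should not set a rule on who goes on wearing lenses. That clinical decision stays with the care provider after study exit.

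The cost is a wording amendment to section 5 and a sentence in the consent letter, plus a correction there if the letter repeats the condition. Sample size, visits and analysis do not change. The downside is that a few more participants may take a pair home.

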6 UNINTENDED EVENTS

The imaging procedures outlined in this protocol will be carried out with instruments that are typically used in any optometric practice and therefore, there are no anticipated or unintended events.

7 DISCONTINUATION FROM THE STUDY

Participants discontinued from a study will be compensated for each attended visit (\$20/hr) in the study. Participants will be discontinued at the discretion of the investigators or participant. The following is a list of possible reasons for discontinuation from the study:

- Screening failure: Participants will be discontinued if they do not meet the inclusion and exclusion criteria outlined in section 4.2.2
- Positive slit lamp finding: Participants may be permanently discontinued from the study depending on the severity of the condition and on the judgement of the investigator.
- Unexpected adverse event: If a participant experiences an adverse event (excessive redness or dryness), at the discretion of the investigator, the participant may be excluded from the study.
- Symptoms: If the participant has persistent symptoms (excessive redness or dryness ascertained by any of the questionnaires or at any visit), the participant may be discontinued from the study based on the clinical judgement of the investigator.
- Disinterest, relocation, or illness: The participant may choose to discontinue due to reasons within or beyond their control.
- Violation of protocol or non-compliance: The participant will be discontinued if they are unable or unwilling to follow the protocol specified visit schedules and/or study procedures.
- Lost to follow-up: The participant will be discontinued if they cannot be contacted and does not return for a final exit visit, and if the investigator has made a reasonable effort to contact the participant for a final study visit.
- Premature termination of the study by the Office of Research Ethics at the University of Waterloo.

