4.2 STUDY POPULATION

4.2.1 SAMPLE SIZE CALCULATION

A minimum sample of 20 DE participants are required to complete the study and thus 25 DE participants will be enrolled. The standard deviation used to determine the sample size was derived from a previous study involving a comparison of fitting scleral contact lenses of different vaults in keratoconus patients and from evaluation of cornea thickness in controls and those having keratoconus (a plausible comparative group).

Power (i.e. the probability of correctly rejecting the null hypothesis) required for this study/experiment is 90% and type-I error is set to 0.05.

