9 STATISTICAL ANALYSIS AND DATA MANAGEMENT

9.1 STATISTICAL ANALYSIS

All data described above will be analysed at the University of Waterloo from the eyes wearing the scleral lenses. Data analysis will be conducted using Statistica 13. Descriptive statistics will be used to analyse the baseline variables (age, gender, sagittal depth distribution, etc.). Table 3 lists the primary outcome variables and anticipated statistical procedures.

Table 3: Statistical procedures

| Variable | Analysis | Statistical test |
|---|---|------------------------------------|
| Parametric: tear clearance, corneal thickness, epithelial thickness, curvature, vision, osmolarity, comfort ratings | Comparison of lenses 1, 2 Comparison of epithelial and corneal thickness evaluation, osmolarity measurements | Paired t-test ANOVA RM-ANOVA |
| Nonparametric: OSDI, SPEED, CLDEQ-8, levels of protease | Comparison of ocular symptoms, quality of life, dryness, subjective assessment | T-test Mann-Whitney U test |

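### Participants can be discontinued for dryness, an outcome of the trial, and Section 9.1 names no analysis that handles loss depending on the outcome

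*Combined protocol and SAP*

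**What the plan says.** - **Discontinuation.** Section 7 covers persistent symptoms ("excessive redness or dryness ascertained by any of the questionnaires or at any visit") and adds that "the participant may be discontinued from the study based on the clinical judgement of the investigator". A second route rests on the same symptoms: "If a participant experiences an adverse event (excessive redness or dryness), at the discretion of the investigator, the participant may be excluded". No threshold is given for either.
- **Outcomes.** Section 3 lists "Contact Lens Questionnaire-8 (CLDEQ-8) questionnaire score" among the primary outcomes and "Subjective ratings of comfort, dryness, vision and burning" among the other variables.
- **Design.** Section 4.1.1 describes a "prospective, dispensing cross over study design involving five visits", with the two lenses worn in random order.
- **Sample size.** Section 4.2.1 states "A minimum sample of 20 DE participants are required to complete the study" and enrols 25.
- **Analysis.** Table 3 in Section 9.1 names "Paired t-test ANOVA RM-ANOVA" for the row with thickness, osmolarity and comfort ratings. The row with CLDEQ-8, protease and the dryness comparison is given a t-test and a Mann-Whitney U test, neither described as paired.
- **Form handling.** Questionnaires filled in at home are handed in at the four-week follow-up visit (Sections 4.3.11, 4.5.2 and 4.5.3). Nothing is said about collecting them from someone who is discontinued earlier.
- **Not stated.** There is no analysis population, missing-data method or outcome collection at discontinuation.

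**The concern.** In a crossover each participant serves as their own control. If a high dryness score leads to discontinuation, the people removed are not a random subset: the drier lens triggers more of the losses. A paired t-test or a classical RM-ANOVA then discards such a person altogether, including whatever was recorded on the first lens. A real difference between coated and uncoated lenses can be understated, and the result describes those who tolerated both lenses, not those who were randomised. Enrolling 25 to finish with 20 protects the number of pairs. It does not protect against this selection.

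**Working it through.** **Inputs from the plan.** 20 completers, 25 enrolled, power 90%, type-I error 0.05 (Section 4.2.1). No SD, effect size, sidedness or dropout rate is given.

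**The plan's own figures.** 25 enrolled for 20 completers implies a loss of 5/25 = 20%, and 20/(1 − 0.20) = 25. The 20 itself cannot be rebuilt without an SD and an effect. Taking a two-sided test, 20 pairs with 90% power correspond to a standardised paired difference of 0.764 (noncentral t). That value is used below only as an illustration.

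**Illustrative model (assumed, not from the documents).** Symptom scores on the two lenses are bivariate normal with SD 1. The worse lens has mean 0 and the better lens lies d lower, with d = 0.764 × √(2(1 − ρ)). This gives d = 0.764 for within-person correlation ρ = 0.5 and 0.592 for ρ = 0.7. Order is random. A participant leaves when a score passes a cut of 0.8 or 1.0 SD.

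**Ratio of the estimated to the true lens difference**

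| Loss rule and analysis | ρ = 0.5 | ρ = 0.7 |
|---|---|---|
| Loss in either period before the endpoint; completers, paired | 0.83-0.86 | 0.87-0.90 |
| Loss only after a high recorded period-1 score; completers, paired | about 0.94 | about 0.96 |

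The first rule keeps 76-83% of participants. The second loses 10-15%. Under the second rule two further analyses were run, across both correlations:

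- An unpaired comparison of all available scores gives 1.06-1.10.
- A likelihood analysis of all available scores gives 1.00.

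**Why the direction differs.** Under the second rule, someone with a high score on the worse lens in period 1 stays in that lens's average. Their second-lens score, which would also tend to be high, is missing from the better lens's average. The better lens then looks too good and the unpaired gap widens.

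**Second set of assumptions.** With true differences of 0.3-0.8 SD, correlations of 0.3-0.7 and loss possible in either period:

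- The completers' difference is 5-12% too small at 8% loss (2 of 25) and 10-22% too small at 20% loss (5 of 25).
- For a true difference of 0.50 SD at 20% loss, completers show 0.39-0.44. A likelihood analysis that includes the score at discontinuation returns 0.50.
- For a difference of 0.8 SD and correlation 0.3, power is 90% with all 25, 82% with 20 after random loss and 73% with 20 after dryness-driven loss.
- With no true difference, the lens-versus-lens bias is zero and the type-I error stays at 5%.

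All these figures apply to an outcome that is itself the trigger. For thickness or osmolarity the distortion depends on how closely each tracks dryness.

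**The case against.** A reader might infer that the plan restricts the analysis to completers, that the worst results on the drier lens are always deleted, and that every comparison is pulled toward no difference by 10-17%. The documents do not support that reading.

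- **No completers-only rule is written.** Section 4.2.1 sets a recruitment target, not an analysis set. The restriction follows from what a paired test needs and from the silence on missing data.
- **Table 3 does not assign the paired tests to CLDEQ-8 or dryness.** Unpaired tests would keep a one-lens score, and the bias can then run away from no difference.
- **Timing limits the questionnaire route.** Forms arrive at the four-week visit, when that lens's endpoints are measured. Discontinuation at visit 1-2 loses only the second lens, and at visit 2-2 it loses nothing. This favours the milder figures.
- **The frequency is unknown.** The rule is discretionary, and Section 7 lists eight reasons for discontinuation with no share for dryness. The implied 20% loss is not a forecast of dryness dropout. The 0.764 comes from a calculation whose SD relates to lens vault and corneal thickness, not symptoms.
- **Masking** of investigator and participant limits deliberate selection.

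All of this stands, but it does not remove the point. Section 7 allows the symptom to be found at any visit and Section 4.4.7 allows unscheduled visits, so loss before the endpoint is possible. Masking does not stop selection through the symptom itself. The unpaired tests have no planned four-week value from someone stopped mid-period, and they give up the pairing for which the crossover was chosen.

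**Conclusion.** The concern holds in a limited form. Loss may depend on the outcome, and none of the tests named in Section 9.1 deals with it. The paired tests shrink a real difference in outcomes related to dryness, while the unpaired tests can exaggerate one. The bias ranges from roughly 4-6% of the true difference, if loss follows a recorded period-1 score, to 10-17% if it can precede the endpoint in either period. Both ranges rest on assumed normal scores, a hard cut-off and correlations of 0.5-0.7. The actual size cannot be derived from the documents. The bias can mask or distort a real lens difference, but under these assumptions it does not create one where the lenses are equal. The change should be made because it is cheap and gives a better estimate, not because the plan is shown to fail.

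**What to change.** Leave the clinical stopping rule as it is, and amend the analysis and data-collection text.

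1. **Section 9.1, main analysis.** Analyse everyone dispensed at least one lens with a linear mixed model: lens, period and sequence as fixed effects and participant as random effect. Use all available scores, including the weekly CLIQ and the biweekly CLDEQ-8 (frequencies as in Section 4.5.1).
2. **Section 7 or 4.5.3.** State that forms already completed are retrieved when a participant is discontinued. The model removes the bias only if the triggering score is recorded. If that score is missing, the model does not in general correct for it.
3. **Reporting.** Tabulate discontinuations for dryness or redness by lens.
4. **Sensitivity analysis.** Keep the completers' paired test.

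The cost is one extra model and the retrieval of forms that are already scheduled. With complete data the result will be close to the paired analysis. It need not be identical, because the model includes a period term and 25 participants cannot split equally between two orders.
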